SAFETY EVALUATIONS	
Safety Evaluations:
 
 1. Incidence of acute AE will be monitored. 2. Continuous patient monitoring and recording of vital signs (pre-, during, and at least 30 min-post contrast agent injection) will be provided by expert and specialized staff, including pediatric anesthesiologists and /or staff from the UCLA Neonatal or Pediatric Intensive Care Units. 3. Incidence of other AE up to 60 days post-MRI via a medical record review. 
Procedures to Reduce Risks of Feraheme Infusion:
 
 1. All patients will be screened for contraindications to Feraheme® administration, including a history of allergy to intravenous iron products and iron overload. 2. Performing MRI in newborns to 6 years of age under sedation and/or general anesthesia with airway protection is considered the standard of care at most institutions performing pediatric cardiac MRI for this age group. In the case of a clinically urgent or life-threatening AE during the procedure, there will already be in place full airway protection and support of respiration.

	
3. Patients will undergo continuous monitoring of heart rate, blood pressure, oxygen saturation and ECG tracing for the duration of the MRI procedure and, at a minimum, 30 min after the injection. In the case of a clinically important AE, changes in vital signs will be evident immediately and appropriate treatment initiated. Protocols are in place to deal with acute AEs related to hypersensitivity and/or anaphylaxis.
 
4. The dose of Feraheme® will be up to 4 mg /kg (approximately half the single therapy dose), diluted with saline and infused slowly per FDA guidelines.

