4.4 Safety Concerns with GBCAs

GBCAs have been used for over a quarter of a century and have a highly favorable safety profile, which is predominantly based on their stability *in vivo*. GBCAs are chelates designed to tightly bind gadolinium ions because free gadolinium ions are toxic (16). In recent years, some safety concerns have been raised relating to the association of nephrogenic systemic fibrosis (NSF) with GBCA exposure for patients with renal impairment, and observation of gadolinium deposition in brain tissue, even in patients with normal renal function (17–22). The gadolinium deposition in tissue may be particularly worrying in children because of their projected life-expectancy and in whom Gd may potentially persist indefinitely. Furthermore, there are concerns of hypersensitivity to GBCA injections (23,24) and association of Ablavar with prolongation of the QT interval on the ECG, which may pose more concern for cardiac arrhythmias in children with CHD than those with normal hearts.

[Nephrogenic systemic fibrosis (NSF)] In 2006, associations between NSF and GBCA exposure (25,26) led to a boxed warning alert by the US FDA (27) and the EMA (28) to restrict the use of GBCAs in patients with renal insufficiency. Autopsy studies have reported the presence of gadolinium in skin, heart, blood vessels, lungs, lymph nodes, spleen, liver, kidney, and dura of patients with NSF (16). Almost a decade later however, the pathophysiology of NSF remains unclear. Nevertheless, a consistent body of literature does suggest that slow clearance of GBCAs in patients with impaired renal function predisposes to transmetalation with release of free gadolinium ions, which have fibrogenic effects (29). The diagnosis of NSF is complex (30) and should only be made when clinical and histopathological criteria set forth by the Yale NSF Registry are met (31). NSF is described as skin discoloration and swelling progressing to erythematous papules, brawny lesions, and subcutaneous sclerosis (32,33) and occurs within 2-3 months of exposure to GBCAs, but late onset cases have been reported (34). Recently, a new entity, termed gadolinium-associated plaques, was reported in two patients by Gathings et al. (35), whereby neither patient had NSF while only one patient had renal failure. Both patients, however, had erythematous plaques associated with sclerotic bodies thought to be pathognomonic for NSF. This occurrence was related to gadodiamide.

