Zou et al. (33) in their review of 370 biopsy confirmed cases of NSF, suggest that eliminating risk factors may substantially reduce the risk of NSF without having to shift to other imaging modalities, which may incur risk of radiation and iodinated contrast-induced nephropathy. These preventable risk factors include using the lowest dose possible for diagnostic result (limiting GBCA dosage to $<0.1\text{mmol/kg}$), avoiding non-ionic linear GBCAs in those on dialysis or having $\text{eGFR} < 30\text{mL/min/1.73m}^2$, dialyzing dialysis-dependent patients promptly after exposure, and delaying GBCA administration in the setting of acute renal failure particularly when proinflammatory conditions may exacerbate oxidative stress. The Contrast Media Safety Committee of the ESUR (29) also recently published recommendations for NSF-risk mitigation where they outlined the level of evidence and identified classes of recommendations for clinical practice. For the pediatric population, no specific evidence based-guidelines exist. Guidelines for adults are typically used. There have been 10 biopsy-proven pediatric cases of NSF, but since the implementation of guidelines, no new cases in children have been reported (38). To date, no cases of NSF have been reported in very young children (38). However, it is known that children younger than 2 years have immature renal function (39). The glomerular filtration rate (GFR) of pre-term and term newborns can be as low as 40 ml/min/1.73m^2 , and it gradually increases to 66 ml/min/1.73m^2 at 2 weeks after birth (39). Due to concerns about nephrogenic systemic fibrosis (NSF), The European Society of Urogenital Radiology warns against the use of GBCA, including gadofosveset, in children less than 1 year old (40). **Therefore, a significant portion of the children in our study will have immature renal function with an unknown, but likely very low risk of developing NSF.**

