7 STUDY DESIGN

7.1 Study Overview

This is an exploratory, investigator-initiated, prospective, open label, case-control, single center, phase IV study that will examine the diagnostic effectiveness of Feraheme® as an MRI contrast agent in pediatric patients with CHD. A total of 120 patients with suspected or known CHD (age newborn to 6 years) of all ethnicities, females and males, will be enrolled. Total duration of subject participation in the imaging study will be approximately 1.5 hours. In general, we expect the pediatric MRI scans to take no more than about 60 minutes once the scan begins. We will also follow up the children for up to 60 days. Total duration of the study is expected to be 5 years. Our study has two parts:

1) Part I is a comparison study between Feraheme®-enhanced MRI and Ablavar®-enhanced MRI. The goal of Part I is to compare the diagnostic efficacy of these two contrast agents for pediatric CHD using our validated technique MUSIC-MRI (1). We hypothesize that Feraheme® provides superior diagnostic effectiveness than Ablavar® for these patients. The duration of Part I is expected to be 3 years.

2) Part II is expected to commence after the statistical significance of the primary endpoint of Part I is confirmed and the goal is to determine the diagnostic efficacy of an MRI pulse sequence (self-gated MUSIC-MRI), which will leverage advanced image reconstruction techniques and

respiratory motion compensation strategies. Self-gated MUSIC-MRI may ultimately enable high-quality free-breathing cardiovascular MRI for pediatric CHD patients who are able to undergo imaging without sedation or general anesthesia (i.e. children >6 years old who can consistently follow verbal instructions during scanning). The duration of Part II is expected to be 2 years.

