12.1 Clinical Assessments

Concomitant Medications

All concomitant medication and concurrent therapies will be documented at the date of study MRI. Dose, route, unit frequency of administration, and indication for administration and dates of medication will be captured.

Demographics

Demographic information (date of birth, gender, race) will be recorded at Screening.

Medical History

Relevant medical history, including history of current disease, other pertinent respiratory history, and information regarding underlying diseases will be recorded at Screening.

Physical Examination

N/A

Vital Signs / Oximetry / Ventilatory Parameters

Continuous heart rate, blood pressure, ECG, pulse oximetry, and end tidal CO_2 will be monitored for the duration of the MRI study and until the subject is recovered or returned to the Intensive Care facility, or for 30 minutes after the infusion, whichever is longer.

Adverse Events

Information regarding occurrence of acute adverse events will be captured throughout the study. Duration (start and stop dates and times), severity/grade, outcome, treatment and relation to study drug will be recorded on the case report form (CRF). Each patient will be followed up via a review of medical record at 60 days after MRI study to capture any additional AEs.

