14.2 Serious Adverse Experiences (SAE)

An SAE is defined as any AE occurring at any dose that results in any of the following outcomes:

- death
- a life-threatening adverse experience
- inpatient hospitalization or prolongation of existing hospitalization
- a persistent or significant disability/incapacity
- a congenital anomaly/birth defect

Other important medical events may also be considered an SAE when, based on appropriate medical judgment, they jeopardize the subject or require intervention to prevent one of the outcomes listed.

Serious Adverse Experience Reporting

The investigators will document all SAEs that occur (whether or not related to study drug). The collection period for all SAEs will begin after informed consent is obtained and end after procedures for the study visit have been completed. In accordance with the standard operating procedures and policies of the local Institutional Review Board (IRB), the site investigator will report SAEs to the IRB.

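### The only planned post-visit safety follow-up, one chart review at day 60, ends about 31 days before the 3-month limit of the protocol's own NSF onset figure

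*Combined protocol and SAP*

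**What the plan says.** Three places set the follow-up period, and they agree.

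- Section 12.1: "Each patient will be followed up via a review of medical record at 60 days after MRI study to capture any additional AEs".
- Section 7.1: "We will also follow up the children for up to 60 days".
- Synopsis, Safety Evaluations: "Incidence of other AE up to 60 days post-MRI via a medical record review". The study flow for both parts repeats the 60-day record review.

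No later visit, call or skin examination is planned, and 12.1 marks physical examination as not applicable. Section 14.2 sets a shorter period for serious events: "The collection period for all SAEs will begin after informed consent is obtained and end after procedures for the study visit have been completed".

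On NSF, section 4.4 says that it "occurs within 2-3 months of exposure to GBCAs, but late onset cases have been reported", and that the diagnosis "should only be made when clinical and histopathological criteria set forth by the Yale NSF Registry are met". It also says that "a significant portion of the children in our study will have immature renal function with an unknown, but likely very low risk of developing NSF". Table 5 lists NSF in renal impairment as a risk of Ablavar and not of Feraheme. Section 9.3 excludes children with eGFR below 40 from Ablavar.

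**The concern.** Objective 3 is to summarize the safety of both agents. The reactions stressed for Feraheme in 5.1 (anaphylactoid reactions and hypotension) are acute and fall under continuous monitoring. The delayed risk named for Ablavar is left to a passive record review that closes before the stated onset period has ended. A case that begins before day 60 may also be missing from the chart at day 60, because diagnosis needs histopathology as well as clinical findings.

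What is at stake is how an empty NSF row in the Ablavar safety table can be read. With a day-60 cut-off it speaks only to events recorded in about the first two months. If Part I is not significant, section 7.3 also asks the DMC to weigh safety differences, including renal risk in these children, when it advises on the agent for Part II.

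The SAE rule adds an inconsistency. An NSF case that led to hospitalization or lasting disability would be serious under 14.2, yet would arise after the 14.2 collection period had closed, whatever the date of the chart review.

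**Working it through.** **The plan's own figure.** The documents give no calculation for NSF or for the 60-day window. The relevant stated figure is the Ablavar group size in 18.7.1, which is the denominator for any NSF count. With difference 1.75, SD 2.10, two-sided alpha 0.025 and 90% power:

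n = 2 × (2.241 + 1.282)² × (2.10/1.75)² = 2 × 12.41 × 1.44 = 35.7, so 36 per group. Allowing for 10% unusable scans, 36/0.9 = 40. The stated figures reproduce.

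**Window against onset period**, at 30.44 days per month:

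- Two months = 60.9 days, so day 60 is 60.9 − 60 = 0.9 days short.
- Three months = 91.3 days, so day 60 is 91.3 − 60 = 31.3 days short.

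**Share of onsets by day 60.** The documents give no onset distribution, so each row is an assumption.

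| Assumed onset | Seen by day 60 | Missed |
|---|---|---|
| Uniform over 0-2 months | 60/60.9 = 99% | 1% |
| Uniform over 0-3 months | 60/91.3 = 66% | 34% |
| Only between months 2 and 3 | 0% | essentially all |

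Late-onset cases would be missed in addition.

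**Chance of seeing no case in 40 children.** With true risk p and captured share f, P(0) = (1 − p × f)^40.

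| True risk p | Full window, f = 1 | f = 0.657 |
|---|---|---|
| 0.01% (assumed) | 99.6% | 99.7% |
| 0.1% (assumed) | 96.1% | 97.4% |
| 1% | 66.9% | 76.8% |
| 7% | 5.5% | 15.2% |

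The last two rows are the range that section 4.4 gives for eGFR below 30, a group excluded from Ablavar here. Expected cases are 40 × 0.001 = 0.04 at 0.1% and 40 × 0.01 = 0.4 at 1%.

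**Upper bound for a zero count.** The exact one-sided 95% bound for 0/40 is 1 − 0.05^(1/40) = 7.2%. It applies to onset within the window observed. If only 65.7% of onsets fall in the window, the bound on total risk is 7.2%/0.657 = 11.0%. If all onsets fall in months 2-3, a zero count at day 60 gives no bound. Section 18.6 pools both parts by agent, so if Part II also used Ablavar, 0/80 would give 1 − 0.05^(1/80) = 3.7%.

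**The case against.** The strongest case against this point is that group size and low risk limit what the trial can say about NSF far more than the window does. At a true risk of 0.1%, going from 66% capture to full capture lowers the chance of seeing nothing only from 97.4% to 96.1%. Section 4.4 also reports no NSF in very young children, and 18.6 rules out inferential analysis of adverse events. All of this stands. A longer window would not turn zero cases into evidence of safety.

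Three stronger readings are tempting, and the documents do not support them.

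- A reader might infer that the Ablavar risk lies largely outside the follow-up. The text says NSF occurs within 2-3 months, which reads as an outer limit. Day 60 may cover part of the period, or most of it.
- A reader might infer that the short window alone would produce a finding of no NSF. Zero cases is the expected result with a complete window too. NSF is neither a safety endpoint in 8.1.3 nor an event of special interest in 18.6, and the plan announces no such conclusion.
- A reader might infer that the DMC would choose the Part II agent on incomplete NSF data. The factors in 7.3 apply only if Part I is not significant, and they direct the DMC to the current literature as well as the trial's own observations.

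Section 15.1 also follows a child withdrawn from treatment for an adverse event until it resolves or stabilizes. That covers known events but does not detect new delayed ones.

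**Conclusion.** The mismatch is real and rests on the protocol's own figures: review at day 60, against an onset period that runs to about day 91 with later cases reported. The share missed cannot be determined from the documents. It runs from about 1% to essentially all, depending on an onset distribution that they do not give. An absence of NSF at day 60 therefore does not cover the period the protocol describes.

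The size of the problem is modest. At a risk of 0.1% or less, zero cases among 40 children is at least 96% likely with any window. The gain from a later review is a safety summary that spans the stated onset period and a somewhat better chance of catching a rare serious event. It does not provide a rate comparison. No sample-size or power figure changes. The text of 14.3 (Medical Monitoring) was not available, so the conclusion rests on the other sections. The point is worth acting on because the change is inexpensive.

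**What to change.** 1. In the synopsis (Safety Evaluations and study flow), 7.1 and 12.1, move the record review past the stated 3-month onset figure for all children in both groups, for example to about 120 days, which is 120 − 91.3 = 28.7 days beyond it. That date is one reasonable choice, and no practical window covers all late onset.
2. Have the review look specifically for new skin or fibrotic findings.
3. Record the onset date of each adverse event, so that events from days 0-60 can still be tabulated.
4. Reconcile the SAE collection period in 14.2 with the adverse event review period.
5. In 18.6, report any zero count with its upper bound (7.2% one-sided for 0/40), and state that later-onset NSF and rare risks cannot be excluded.

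The cost is small: the same chart review done later, with no added visit or procedure. Final safety data would arrive about two months later (120 − 60 = 60 days), and more unrelated background events, such as surgical ones, would be captured in both groups. If the sponsor keeps day 60, the protocol should at least say that this review cannot assess NSF or other delayed gadolinium effects.

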12.2 MRI Procedures

12.2.1 Patient Preparation and Setup

All patients will undergo MRI on an FDA approved, clinical 18-channel Siemens 3.0T Magnetom TIM Trio scanner, and running version B17 software. The appropriate RF receiver coil configuration will be chosen depending on patient size; for example neonates may be studied using a 16 element adult knee coil, infants using an adult head-neck coil combination and older children using surface flex coils or a body array coil. Fixed (spine) coil elements in the patient table may be used in combination with any of the other coils (except the knee coil).

Prior to Feraheme or Ablavar infusion, all patients will be asleep, intubated and ventilated such that, in the case of a clinically urgent or life-threatening AE, there will already be in place full

airway protection, physiological monitoring and support of respiration. Consistent with institutional clinical practice at UCLA, anesthesia in the pediatric CHD patients will be performed by specialized pediatric anesthesiologists regardless of contrast agent used (Feraheme vs. Ablavar) with continuous monitoring of heart rate, blood pressure, pulse oximetry, end tidal CO₂, and, where appropriate, anesthetic gas levels (such as sevoflurane). In the case of a SAE, changes in vital signs will be recognized immediately and appropriate treatment initiated. All of the children in our study will have protected airways and mechanical ventilatory support from the start of the procedure to the end. Serious adverse reactions to any agent may include laryngeal edema and bronchospasm, where prior endotracheal intubation may be lifesaving. Should other events occur involving changes in heart rate, heart rhythm and /or blood pressure, the anesthesiologist can focus his / her attention on the appropriate use of chronotropic or inotropic agents, intravenous fluids and /or vasoactive drugs, without having to secure the airway. All patient physiological monitoring data are, and will continue to be, digitized and transferred in real time to the electronic patient medical record, where they are stored permanently and retrievably. Relevant abstractions from these and other patient safety data (protected health information removed) will be included in our DMC, IRB and IND adverse event reports.

Once asleep and intubated, patients will be positioned in the appropriate receiver coils and monitored with ECG and with MRI compatible pulse oximetry and non-invasive blood pressure measurement (InVivo Medical Solutions, Inc.). The vital signs monitoring equipment will all be FDA approved devices. The end-tidal CO₂ line will be interfaced via a three way plastic stop-cock to the respiratory port of the MRI physiological monitoring unit. In this way, the respiratory signal is split so as to provide both uninterrupted end-tidal CO₂ monitoring and airway pressure signal. The airway pressure trace is available for use as a respiratory gating signal to compensate for respiratory motion artifact without interrupting patient ventilation (1).

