	
Part I:
 
The image quality score for each individual anatomical structure will be compared between the two contrast agents.
 
 1. Image quality score at the aortic root. 2. Image quality score at the main pulmonary artery. 3. Image quality score at the coronary arteries. 4. Image quality score at the out-flow tracts. 5. Image quality score at the valves. 6. Image quality score at the ventricular chambers. 7. Image quality score at the atria. 8. Sharpness value at the interventricular septum. 9. Sharpness value at the ascending aorta. 
A parametric two-sided t-test will be performed after an appropriate transformation of individual score if needed. Similarly, the sharpness values and the CNR will be compared between the two groups using a two-sided t-test.
 
Part II:
 
The image quality score for each individual anatomical structure will be compared between the two techniques (ventilator-gated MUSIC-MRI vs. self-gated MUSIC-MRI). A paired t-test will be used to determine the difference in image quality scores using appropriate transformation if needed. Similarly, the sharpness values and the CNR will be compared between the two groups using a two-sided t-test.
 
SAFETY EVALUATIONS:
 
Safety will be assessed through summaries of adverse events, vital signs recordings, and any relevant clinical laboratory test data (including change from baseline). Safety analyses will include all patients who receive any amount of study drug (safety population). All adverse events will be coded using the Medical Dictionary for Regulatory Activities (MedDRA). Descriptive statistics will be used rather than inferential statistics.
 
An independent DMC will monitor the safety data on an ongoing basis in this trial and will review data from a pre-specified interim analysis.

ABBREVIATED STUDY FLOW	
Part I:
 
 1. Patient is referred for cardiovascular MRI after inconclusive echocardiography exam. 2. The Investigators discuss with the patient's legal guardian(s) the study design and risks/benefits for Feraheme and Ablavar administration.

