8.1.2 Secondary Endpoints

A statistically significant difference in image quality scores in each of the 7 important anatomical structures between Feraheme®-enhanced vs. Ablavar®-enhanced ventilator-gated MUSIC-MRI.

A statistically significant difference in sharpness measurements at the ascending aorta and the interventricular septum.

A statistically significant difference in blood-myocardium CNR measurements.

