
muscles and trabeculae, 4=chambers clearly distinguishable with excellent wall definition and with clear definition of the papillary muscles and trabeculae.

Image Sharpness Values: Objective image sharpness will be measured through the interventricular septum and ascending aorta using a previously described method (1). The image sharpness scores will be measured by drawing a linear signal profile and calculating the slope of the signal intensity curve. The slope is defined as the image intensity difference divided by the distance between the two points at 20% and 80% of the dynamic range, respectively.

Blood-Myocardium CNR: The blood-myocardium CNR will be measured by drawing three regions of interest (ROI), one at the center of left ventricular (LV) cavity, one at the interventricular septum and one in the background air region. The CNR will be calculated as the difference in mean signal intensity between the LV cavity ROI and the septum ROI divided by the standard deviation of the background air ROI signal.

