18.5 Secondary Efficacy Endpoints

18.5.1 Part I – Differences in individual image quality score (per segment or structure), image sharpness values, and CNR measurements for Feraheme vs Ablavar

The secondary efficacy endpoints for Part I are the individual image quality score for each of the seven anatomical structures as defined in 18.3, the image sharpness values for the ascending aorta and the interventricular septum, and the CNR measurements for each contrast agent. Data will be tested for normality using the Shapiro-Wilk and Shapiro-Francia tests. The average image quality scores of each anatomic structure between two readers, the image sharpness values, and the CNR measurements will be compared using a parametric two group t-test with an appropriate transformation if needed. If the data are not normally distributed and transformation is not possible, a non-parametric Wilcoxon-rank-sum test will be considered. Kappa statistics will be reported between two independent scores in each secondary endpoint.

18.5.2 Part II – Differences in individual image quality score (per segment or structure), image sharpness values, and CNR measurements for ventilator-gated vs self-gated MUSIC-MRI

The secondary efficacy points for Part II are the individual subjective image quality score for each of the seven anatomical structures as defined in 18.3, the image sharpness values for the ascending aorta and the interventricular septum, and the CNR measurements for the two MRI techniques. Data will be tested for normality using the Shapiro-Wilk and Shapiro-Francia tests. The average image quality scores of each anatomic structure between two readers, the image sharpness values, and the CNR measurements will be compared using a paired t-test with the margin of non-

inferiority of 0.75 for the image quality scores. If the data are not normally distributed and transformation is not possible, a non-parametric Wilcoxon-rank-sum test will be considered. Kappa statistics will be reported between two independent scores in each secondary endpoint.

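### Part I compares CNR between agents with an unadjusted two-group test although the receiver coil follows body size; record the coil and put it in the model

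*Combined protocol and SAP*

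**What the plan says.** - **Coil (12.2.1).** "The appropriate RF receiver coil configuration will be chosen depending on patient size". By way of example, "neonates may be studied using a 16 element adult knee coil, infants using an adult head-neck coil combination", with surface flex or body array coils for older children. "Fixed (spine) coil elements in the patient table may be used in combination with any of the other coils (except the knee coil"). Section 12.2.2.1 gives a possible weight range of 1 to 20 kg.
- **CNR (18.3).** The difference in mean signal between the LV cavity and the septum, "divided by the standard deviation of the background air ROI signal". There is no adjustment or normalisation for coil.
- **Role (8.1.2).** "A statistically significant difference in blood-myocardium CNR measurements" is a Part I secondary endpoint, one of the ten listed in the synopsis.
- **Test (18.5.1).** "CNR measurements will be compared using a parametric two group t-test with an appropriate transformation if needed", with a Wilcoxon rank-sum test considered if normality fails and no transformation works. The synopsis likewise says that "the sharpness values and the CNR will be compared between the two groups using a two-sided t-test". Neither place names a covariate, stratum or matching.
- **Allocation (7.2, 11.1.1).** Guardians choose the agent. Families who defer are placed in whichever group is under-enrolled. Size, age and coil play no part.
- **Data recorded (12.1).** Coil is not listed.

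**The concern.** The two Part I groups are different children. If the smallest are scanned in one coil and the largest in another, part of the spread in CNR comes from the coil and not from the agent. Two consequences follow.

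1. **Lost precision.** This happens even when both groups have the same coil mix, because between-coil spread goes into the error term.
2. **Bias.** If one agent's group has more small children, the coil contrast enters the agent contrast. It can create a difference or hide one.

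The plan itself makes an imbalance plausible. Section 4.4 says that children under 2 years have immature renal function and reports a European warning against gadolinium agents, including gadofosveset, under 1 year. Guardians choose after the risks of both agents have been explained. That could move the youngest children towards Feraheme, but no figure in the documents shows that it will.

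At stake is one of the few objective Part I measures. Under 7.3, secondary endpoints also enter the DMC's advice on the Part II agent, as one of three factors, but only if the Part I primary comparison is not significant.

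**Working it through.** **1. The plan's own figures.** Section 18.7.1 gives power only for the composite score: difference 1.75, SD 2.10, two-sided level 0.025. Two-sample t power is 62.0% at 20 per group (stated 62%). At 36 per group it is 89.1%, or 90.2% by the normal approximation (stated 90%). Enrolment is 36/0.9 = 40. These figures reproduce. There is no SD, target difference or power for CNR, so only n = 36 per group is carried forward.

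**2. Assumptions (none is in the documents).** CNR is analysed on the log scale with within-coil SD 0.3. There are three coil classes with CNR ratios 1:0.9:0.8, 1:0.8:0.6 or 1:0.7:0.4. The test is two-sided at 0.05 (18.5.1 states no level). The true agent ratio is 1.25 where a difference exists, so δ = ln 1.25 = 0.223.

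**3. Same coil mix in both groups (equal thirds).** The unadjusted SD is s = √(0.3² + v), where v is the variance of the log coil ratios. The noncentrality is δ / (s × √(2/36)), with √(2/36) = 0.2357.

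| Ratios | v | s | Noncentrality | Power, formula | Power, simulated | With coil in model |
|---|---|---|---|---|---|---|
| 1:0.9:0.8 | 0.0083 | 0.314 | 3.02 | 85% | 86% | about 87% |
| 1:0.8:0.6 | 0.0437 | 0.366 | 2.59 | 72% | 72-73% | about 87% |
| 1:0.7:0.4 | 0.1422 | 0.482 | 1.96 | 49% | 48% | about 87% |

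Simulations used 4,000 runs per scenario. With no coil effect, the noncentrality is 0.223/(0.3 × 0.2357) = 3.16 and power is about 87%. The coil factor recovers essentially all of this.

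**4. No true difference, uneven mix.** If the first class's share is higher by k in one group and the third class's share lower by k, the expected log difference is −k × ln(third ratio).

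| Ratios | Mix 40/30/30 vs 20/30/50 (k = 0.20): spurious ratio | False positives | Mix 35/33/32 vs 28/33/39 (k = 0.07): spurious ratio | False positives |
|---|---|---|---|---|
| 1:0.9:0.8 | exp(0.20 × 0.223) = 1.05 | 9% | exp(0.07 × 0.223) = 1.02 | 5% |
| 1:0.8:0.6 | exp(0.20 × 0.511) = 1.11 | 21% | exp(0.07 × 0.511) = 1.04 | 7% |
| 1:0.7:0.4 | exp(0.20 × 0.916) = 1.20 | 36-37% | exp(0.07 × 0.916) = 1.07 | 8% |

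These are simulated rates. The noncentral t formula gives 9.2%, 21.6% and 35.7% for k = 0.20, and 5.5%, 6.9% and 8.6% for k = 0.07. With coil in the model the rate is about 5% throughout.

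**5. Second parameterisation.** CNR was expressed in within-coil SD units, with coil means 0.25, 0.5 or 1.0 SD apart per step and a true agent difference of 0.8 SD.
- Equal mix: unadjusted power 91%, 88% and 73%, against 91-92% adjusted.
- Mild imbalance (25/35/40 vs 40/35/25), no true difference: unadjusted false positives 6.6%, 8.6% and 17.5%, against about 5% adjusted.
- The same imbalance working against the better agent: unadjusted power 84%, 72% and 38%, against about 90% adjusted. This is how a real difference could be hidden.

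**The case against.** **The magnitude is assumed.** This stands. The worst figures need a 2.5-fold CNR range across coils (1/0.4) and a 20-point shift in both end classes. In the mildest balanced case the power loss is about one or two points. When the expected mix is equal, the t-test keeps its nominal level. The adjusted rate of about 5% is also expected, since the fitted model has the form that generated the data.

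**CNR is a ratio, so a gain common to signal and noise cancels.** True. A reader might infer that CNR values from different coils cannot be compared at all. The documents do not support that. What may remain is the effect of real differences in sensitivity and noise, which they do not quantify.

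**The coil list is illustrative.** Section 12.2.1 is worded as examples. The number of configurations actually used is unknown, but selection by size is stated outright.

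**Section 11.1.1 sees no prior reason for parental preference to influence image quality.** That is an assertion and does not discuss size or coil. The Ablavar-only exclusion at eGFR below 40 might suggest that neonates will be missing from that group, since 4.4 says newborn GFR can be as low as 40. Section 9.1, however, does not expect eGFR below 40, so little weight should rest on that route.

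**Efficacy is examined by age category (18.2, 18.6).** These categories roughly follow the coil examples and might reveal a gross pattern. The look is descriptive, the plan calls the study too small for significance in subgroups, and it does not adjust the comparison. Nor would a transformation or a rank test remove a coil offset.

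**Coil nearly stands for body size.** Also true. A coil factor cannot separate the two, although it will absorb some size imbalance as well.

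**Conclusion.** The point holds as a cheap improvement to a secondary analysis. Coil follows size, CNR has no coil correction, nothing balances size between the agents, and the test has no covariate. Any real coil effect therefore costs precision, and bias follows if coil or size mix also differs by agent. The size is unknown: the ranges in the working depend on the assumed coil ratios, the log-SD of 0.3, the mixes and the 0.05 level.

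Two stronger inferences should be resisted. First, the documents do not show that the CNR comparison will be biased, because neither a coil effect nor an imbalance is documented. Second, the point does not touch the primary composite score, its power or the interim rule. Size imbalance in a non-randomised comparison is a wider question than this one. Part II is paired within one session, so coil cancels there provided both scans of a child use the same coil.

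The sharpness slopes in 18.3 share the exposure. They are raw intensity differences over distance, measured with the same coils and tested in the same way.

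**What to change.** 1. Add to the case report form the receiver coil configuration for each scan, including whether spine elements were used.
2. In 18.5.1, analyse log CNR with a linear model containing agent and coil class (knee, head-neck, flex or body array), pooling rare configurations by a rule set before unblinding. Treat the two sharpness slopes in the same way.
3. Report the adjusted agent ratio with its confidence interval beside the unadjusted result.
4. Tabulate coil configuration by agent, so that any imbalance is visible to readers and, if 7.3 applies, to the DMC.

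**Cost.** One added data field, revised wording in 18.5.1 and the synopsis, and about two degrees of freedom for three classes. The adjusted estimate cannot separate coil from body size, and the report should say so. If the coil mix differs greatly between agents, the adjusted interval will widen, which correctly shows how little overlap there is.
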